3.1.1 Study Design: Cohorts

The study will be conducted in 3-5 sites in the United Kingdom.

The study consists of Part A and Part B. Part A includes 3 cohorts with pre-set dosing regimens. Part B includes up to 2 optional adaptive design cohorts whose doses and dosing intervals will be decided based upon the safety, PK, and PD results from Part A available to the unblinded Sponsor. The regimens selected for Part B will not exceed the exposures (i.e., doses and/or dosing intervals) included in Part A.

The study will consist of 3 to 5 cohorts: 3 cohorts in Part A and up to 2 optional cohorts in Part B. Eight subjects will be randomized per cohort (6 active, 2 placebo). A total of approximately 24 to 40 subjects will be enrolled in the study with 24 subjects in Part A and up to 16 in Part B.

Part A

Subjects assigned to Part A will receive one of the following regimens:

Cohort 1 – 3 SC doses of [REDACTED] mg at [REDACTED],

Cohort 2 – 3 SC doses of [REDACTED] mg at [REDACTED], and

Cohort 3 – 2 SC doses of [REDACTED] mg at [REDACTED].

Part B

Part B will consist of up to 2 treatment cohorts. The dose and dosing intervals to be administered to subjects enrolled in these cohorts will be determined by the Sponsor based upon the available unblinded safety, PK, and PD data acquired in Part A. The decision regarding doses and dosing intervals for subjects enrolled in Part B will be made while Part A is still ongoing to allow Cohort 4 in Part B to begin without delay.

Safety Review Committee (SRC) meetings will be convened before administration of the third dose in Cohorts 1 and 2 and before the third dose in Cohorts 4 and/or 5 if a [REDACTED] regimen is selected for those cohorts. Details regarding the SRC and their responsibilities are provided in Section 5.8.

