9.4 Statistical Analyses

9.4.1 General Considerations

All safety, immunogenicity, PK, and PD data will be listed by subject. Unless otherwise specified, baseline is defined as the last observed measurement, whether scheduled or unscheduled, prior to the first dose of study drug.

UPB-101 treatment groups will be defined based on the cohort and dose assignment (e.g., [REDACTED]). The placebo treatment group will include all subjects assigned to placebo and will be pooled according to dosing regimen (e.g., Placebo [REDACTED], Placebo [REDACTED]) or, where appropriate, across all study parts.

No analysis windows will be defined. Data for repeatedly measured endpoints will be analysed according to the nominal visit. Summaries will be grouped by study part to maintain visit alignment across treatment groups.

Continuous variables will be summarized by UPB-101 dose group and pooled placebo, and by dosing frequency with descriptive statistics (e.g., number of observations, mean, standard deviation, median, interquartile range, maximum, and minimum). Categorical variables will be tabulated by frequency and percent of subjects per UPB-101 dose group and pooled

placebo, and by dosing frequency. Demographic data will be summarized by treatment, dose, and dose regimen. Analyses will be based on observed data only; no data will be imputed.

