## 6. STUDY DESIGN

### 6.1. Summary of Study Design

This is a two-part Phase 1, multi-centre randomized, double-blind (Investigator and Subject blinded; Sponsor unblinded), placebo-controlled, multiple ascending dose study to assess the safety, tolerability, immunogenicity, PK, and PD of UPB-101 administered subcutaneous (SC) to adult subjects with asthma.

The study consists of Part A and Part B. Part A includes 3 cohorts with pre-set dosing regimens. Part B includes 2 adaptive design cohorts whose doses and dosing intervals will be decided based upon the safety, PK, and PD results from Part A available to the unblinded Sponsor. The regimens selected for Part B will not exceed the exposures (i.e., doses and/or dosing intervals) included in Part A.

The study will consist of 5 parallel-sequential cohorts: 3 cohorts in Part A and 2 cohorts in Part B. Eight subjects will be randomized per cohort (6 active, 2 placebo). The term 'parallel-sequential cohorts' means that the first 8 subjects will be randomized to Cohort 1. As soon as quota for Cohort 1 has been filled, Cohort 2 will be open to enrolment and so forth. A total of approximately 40 subjects will be enrolled in the study with 24 subjects in Part A and 16 in Part B.

The study includes 4 periods: Pre-Screening, Screening, Dosing, and Observation.

**Pre-screening Period:** Sites may opt to utilize a Pre-screening Informed Consent Form (ICF) to enable performance of a complete blood count (for the absolute eosinophil numbers) in consenting subjects while subjects consider consent for the full study. Pre-screening may not occur more than 90 days before Visit 1.

**Screening Period:** Subjects will be evaluated for eligibility during the 21-day Screening Period before randomization and dosing. Eligible subjects will be allocated to cohorts sequentially and then be randomly allocated to treatment with UPB-101 or placebo in a 3:1 ratio, respectively.

**Dosing Period:** Study drug will be administered SC as follows:

Description of SC Dosing Regimens in Part A			
Cohort	Treatment Arm and Dosage	Number of Injections to Achieve Dose	Frequency x Number of Doses
Cohort 1	UPB-101 [REDACTED] mg	[REDACTED]	[REDACTED]
	Placebo	[REDACTED]	[REDACTED]
Cohort 2	UPB-101 [REDACTED] mg	[REDACTED]	[REDACTED]
	Placebo	[REDACTED]	[REDACTED]
Cohort 3	UPB-101 [REDACTED] mg	[REDACTED]	[REDACTED]
	Placebo	[REDACTED]	[REDACTED]
Description of SC Dosing Regimens in Part B (Adaptive Design)			

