g On dosing visits, chemistry and urinalysis laboratory tests will be collected pre-dose.

h On days where Spirometry is not performed, ACQ-7 question 7 will be answered based on the FEV1 value from the first measurement on the following morning

i Blood sampling for PK on dosing days will be collected pre-dose.

j Plasma levels of IL-5, IL-13, IFN  $\lambda$ , IL-17A, eotaxin-3, IP-10, and TSLP will be measured. Tryptase, carboxypeptidase, and TARC will also be measured.

k Subjects will be contacted by site personnel the day before each visit that includes a spirometric assessment to remind subjects of their visit and study rules. Subjects will also be contacted the day before their admission to the site.

l Flow cytometry samples will be collected and either analyzed or frozen. The decision to assay the frozen samples will be based on previous results.

m At Visit 5 (D2), Visit 6 (D4), Visit 16 (D86), Visit 17 (D88), Visit 18 (D92) and Visit 19 (D99) blood samples for haematology including eosinophils will only be collected for participants enrolled in Cohort 4.

n At Visit 5 (D2), Visit 6 (D4), Visit 16 (D86), Visit 17 (D88), Visit 18 (D92) and Visit 19 (D99) FeNO will be performed only for participants enrolled in Cohort 4.

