## 8. SAMPLE SIZE

The primary objective of the study is to assess the safety and tolerability of UPB-101 when administered as multiple ascending doses. A sample size of 40 subjects with 8 subjects per cohort (6 on active drug + 2 on placebo) is considered sufficient to meet this goal. The sample size is not based on formal statistical hypothesis testing.

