#### 10.1.3. Data Presentation

The full list of TFLs to be produced for the final study analysis are shown in [Section 13](#), and the specific format and content of each data Table/Listing presentation is shown in [Section 14](#).

Summary Tables and Figures will be presented by treatment group (and also for an Overall column including all subjects, for selected data presentations). Within all Tables and Figures values for the treatment groups will be labelled as follows:

- [REDACTED] mg [REDACTED]
- [REDACTED] mg [REDACTED]

- [REDACTED] mg [REDACTED]
- [REDACTED] mg [REDACTED]
- Placebo and/or
- Screen Failures

An Overall column may be included in the disposition, and selected safety outputs which will include all treatment groups (Active and Placebo). Generally, the placebo groups will be pooled across all cohorts however, for some summaries placebo may be summarized according to dosing regimen (e.g. Placebo [REDACTED], Placebo [REDACTED] ) or treatment group (e.g. Placebo [REDACTED]).

For screen failures, data is only expected in a selection of datasets. The data collected within these datasets will be included in the relevant listings only. Additional data that may have been collected for screen failures, in error, will not be displayed in the participants listings. They will not be included in any summary tables.

For selected outputs the dosing regimen may be used in the summaries where cohorts of the same dosing regimen (i.e. [REDACTED], [REDACTED] ) will be grouped together, similarly cohorts may be grouped together by treatment group if there are multiple cohorts with the treatment group (e.g. [REDACTED] [REDACTED]), or summaries may be produced combining all of the active groups together. The ordering of treatment groups shown here represents the order in which they will appear in outputs.

The scheduled protocol visits will be labelled in (applicable) report presentations as follows:

- Screening: Visit 1
- Screening: Visit 2
- Screening: Visit 3
- Day 1
- Day X (where X is the protocol specified Day, to be included within summary Table)
- Week X (where X is the protocol specified study Week, to be included within summary Table)

Generally, the summaries will be produced by Day, although in some cases it may be preferable to summarize by Week. This will be specified within each of the shells, as appropriate.

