### **10.11.1. Biomarkers**

The biomarkers collected in the study include cytokines (IL-5, IFN λ, IP-10, TSLP, eotaxin-3, TARC and lab parameters (Eosinophils, Total IgE and C-reactive protein). Receptor occupancy evaluated by flow cytometry, considered as a biomarker for target engagement, is also included.

All biomarkers, with the exception of the flow cytometry biomarker, will be summarized by visit as absolute values, change from baseline and percentage change from baseline, by treatment group. Any scheduled pre-baseline data will also be summarized by visit and treatment group.

Flow cytometry based evaluation of receptor occupancy (free receptors) will be calculated as the difference between the signal intensity (measured as % of TSLPR+ CD14+ cells) of the test sample and an aliquot of the same sample incubated ex vivo with saturating levels of UPB-101 prior to adding the detection antibody. The receptor occupancy will then be summarized at each visit, along with the percentage of free receptors, where;

% free receptors at any timepoint (t) = (difference between signal intensity at timepoint (t) / difference between signal intensity at baseline )\* 100.

For negative % Free Receptors, set the value to 0. For % Free Receptors greater than 100%, set the value to 100%.

For all biomarkers the baseline will be the last non-missing result prior to first dose.

Any data that is below the limit of quantification will be replaced with zero before summarising but will be listed as '<BLQ'.

A mean plot of the biomarker results over time will be displayed, where the plots will display the mean at each visit +/- the standard error, with a line per treatment group.

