### **10.11.2. Spirometry**

FeNO and other spirometry parameters (FEV1, FEV1%, FVC and PEF) will be summarized by visit as absolute values, change from baseline and percentage change from baseline, by treatment group. Any scheduled pre-baseline data will also be summarized by visit and treatment group.

Plots of the mean over time will be displayed for each of the spirometry parameters listed above and all spirometry parameters collected will be included within subject listings.

Baseline for spirometry will be defined as the 60-minute pre-dose values at Visit 4. On all other dosing days the values recorded at 60 minutes pre-dose will be summarized. In case of multiple measurements at 60 minutes pre-dose (unexpected), the average of these will be used for baseline and the best (maximum) of these values will be used at the post-baseline timepoints. On all non-dosing post-baseline days the best (maximum) of the 2 measurements performed will be summarized.

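### The pooled placebo line in the eosinophil and FeNO mean plots runs through visits at which only some cohorts are tested, so it can move when no subject has changed

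*SAP*

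**What the plan says.** **The plots.** For the biomarkers, which include eosinophils, SAP 10.11.1 states: "A mean plot of the biomarker results over time will be displayed, where the plots will display the mean at each visit". The sentence goes on to add standard-error bars and one line per treatment group. FeNO is handled in SAP 10.11.2: "Plots of the mean over time will be displayed for each of the spirometry parameters listed above". That section mentions neither lines nor bars, and SAP 10.1.3 says only that figures are shown by treatment group. The figures are 14.2.2 (labs) and 14.2.4.1 (spirometry, including FeNO).

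**Placebo.** SAP 10.1.3: "Generally, the placebo groups will be pooled across all cohorts". It allows placebo by regimen or by treatment group for some summaries and does not say which.

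**Sampling days.** Footnote m to the SAP schedule says of six visits (D2, D4, D86, D88, D92, D99) that "blood samples for haematology including eosinophils will only be collected for participants enrolled in Cohort 4". Footnote n makes the same restriction for FeNO. SAP Table 3, which covers the schedule of Cohorts 1 and 2, has eosinophils on D36 and D71. SAP Table 5, used for Cohorts 3 and 4, has no D36 visit and no haematology on D71.

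**The protocol's rule.** Protocol 9.4.1: "Summaries will be grouped by study part to maintain visit alignment across treatment groups". The SAP does not repeat this, and SAP Section 11 does not list it as a change.

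**The concern.** A line drawn through group means is read as the course of one group over time. Here the pooled placebo line would be the mean of one set of people at one visit and of a quarter or half of them at the next. Differences between people then appear as movement over time.

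The line beside it does not behave this way. The Cohort 4 active group follows a single schedule, so its planned six subjects are the same at every point. Its comparator falls to the two Cohort 4 placebo subjects on D2 and D4 and returns to the full pool on D8. An apparent early separation from placebo, or the lack of one, could come from who is in the placebo mean.

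The SAP plans no formal testing, so the PD results will be read from descriptive tables and figures.

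**Working it through.** **1. The plan's own count.** SAP Section 8: "A sample size of 40 subjects with 8 subjects per cohort (6 on active drug + 2 on placebo". Five cohorts × 8 = 40, which reproduces the stated total. Pooled placebo is 2 × the number of cohorts: 10 for five, 8 for four, 6 for three.

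**2. How many cohorts.** The documents differ. SAP 6.1: "The study will consist of 5 parallel-sequential cohorts: 3 cohorts in Part A and 2 cohorts in Part B". Protocol 3.1.1: "The study will consist of 3 to 5 cohorts: 3 cohorts in Part A and up to 2 optional cohorts in Part B". SAP 10.1.3 lists four active labels, so four cohorts is the base case below.

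**3. Planned placebo n by visit,** counted from SAP Tables 2, 3 and 5 with footnotes m and n:

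| Days | Cohorts tested | Eosinophils | FeNO |
|---|---|---|---|
| D1, D8, D15, D29, D57, D85, D113, D141, D169, D197, D225 | 1–4 | 8 | 8 |
| D2, D4, D86, D88, D92, D99 | 4 only | 2 | 2 |
| D36, D71 | 1 and 2 only | 4 | not scheduled |

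Eosinophils have 19 visits, 8 of them partial, and n changes on 8 of the 18 line segments. FeNO has 17 visits, 6 of them partial, and n changes on 4 of 16 segments.

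**4. Other cohort counts.** With Cohort 5, the full n is 10. Eosinophils switch between 10, 6 and 2, or between 10, 4 and 2, depending on its schedule; FeNO switches between 10 and 2. With Part A alone, eosinophils switch between 6 and 4, and FeNO stays at 6.

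**5. Size of the false step.** Suppose that absolute values are plotted, no subject changes, and the between-subject SD is σ. The SD of (mean of k of the N subjects − mean of all N) is σ√(1/k − 1/N).

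- 8 to 2: σ√(1/2 − 1/8) = 0.61σ
- 8 to 4: σ√(1/4 − 1/8) = 0.35σ
- 10 to 2: σ√(1/2 − 1/10) = 0.63σ

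The documents give no SD, so a range is assumed: lognormal values with log-scale SD 0.4 to 0.7, which is a CV of √(exp(0.4²) − 1) = 0.42 to √(exp(0.7²) − 1) = 0.80. Simulating 200,000 sets of eight constant subjects gives:

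| Switch | Median shift in placebo mean | Probability of a shift above 20% |
|---|---|---|
| 8 to 2 | 17% to 30% | 0.42 to 0.66 |
| 8 to 4 | 10% to 18% | 0.16 to 0.44 |

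**6. An invented illustration.** Let the two placebo subjects in Cohorts 1, 2, 3 and 4 sit constantly at 250, 300, 350 and 450 cells/µL. The mean of all eight is (250 + 300 + 350 + 450)/4 = 337.5. On D2 the plotted mean is 450, and on D36 it is (250 + 300)/2 = 275. Nobody has changed.

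**7. Would grouping by study part be enough?** No. Part A placebo for eosinophils would be 6 at common visits and still 4 on D36 and D71. Part B with Cohort 4 alone would be 2 throughout. Restricting the joined line to the 11 common visits gives n = 8 at each of them for both markers.

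**The case against.** **The scale is not fixed.** A reader might infer that the SAP prescribes plots of raw values. It says only results, or the mean over time. Absolute values are the natural reading, because change from baseline is named separately for the summaries, but they are not specified. If change from baseline were plotted, the step with no subject changing would be zero. This stands, and step 5 depends on the scale. Changing membership would still affect the line once subjects do change. The Section 14 shells are not shown and might add detail.

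**Other displays already protect the reader.** Tables 14.2.3.2.1.1, 14.2.3.2.1.2, 14.2.3.4.1.1 and 14.2.3.4.1.2 give change and percentage change from baseline, and SAP 10.1.3 puts n first among the statistics. The biomarker plot also carries standard-error bars, which for a given SD would widen by √(8/2) = 2.0 or √(8/4) = 1.41. This also stands, and it confines the problem to the figures. Wider bars signal lost precision but do not show that the subjects differ.

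**Pooling is permitted.** A reader might infer that pooling placebo across cohorts itself breaks the protocol. Protocol 9.4.1 allows pooling across all study parts where appropriate. What is undeclared is the loss of the visit-alignment rule, and step 7 shows that restoring it would not be a cure.

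**Stronger readings that the documents do not support:**

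- *FeNO also drops to 4.* It has no D36 or D71 assessment in any cohort.
- *Total IgE is worse, with adjacent points from entirely different subjects.* The printed row for Cohorts 1 and 2 has IgE on D36 and not on D29 or D57, unlike CRP and FeNO. That may be a misprint or a shift from text extraction, so no size is claimed.
- *The cohorts attend different visits on D2 and D4.* All cohorts attend; only Cohort 4 has these two tests.
- *The D2 and D4 samples were added to show onset, and these figures set the dose and interval.* SAP Section 4 says only that timepoints were added to evaluate the PD effect. Part B regimens are chosen by the unblinded sponsor during Part A, and dose- and exposure-response modelling is separate (Protocol 9.4.8).

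**Conclusion.** The point holds as a minor defect in exploratory figures. Under the SAP's default rules, the pooled placebo line for eosinophils and FeNO mixes visits with different subject sets, beside a Cohort 4 active line whose planned membership is fixed. The switch in n follows from the schedules under every cohort count for eosinophils, and for FeNO whenever Cohort 4 runs. The percentage shifts rest on three assumptions: absolute values are plotted, placebo is pooled across all cohorts in these figures, and the between-subject CV is 0.42 to 0.80. The primary safety analysis and the by-visit tables of change from baseline are not affected.

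**What to change.** In SAP 10.11.1 and 10.11.2, for Figures 14.2.2 and 14.2.4.1:

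- State the scale, and plot change or ratio from each subject's own baseline.
- Join the pooled placebo line only across visits scheduled for every pooled cohort: D1, D8, D15, D29, D57, D85, D113, D141, D169, D197 and D225. Recheck this list if Cohort 5 runs.
- Show cohort-only visits as unjoined points, against placebo from the cohorts tested on that day.
- Print n under each visit.

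In SAP Section 11, state that the grouping by study part for visit alignment in Protocol 9.4.1 is not followed, and why. Separately, confirm the total IgE visit days in the schedule for Cohorts 1 and 2.

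The cost is SAP wording and some figure programming. No new data are needed, and the figures become slightly busier.

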### **10.11.2. Spirometry**

FeNO and other spirometry parameters (FEV1, FEV1%, FVC and PEF) will be summarized by visit as absolute values, change from baseline and percentage change from baseline, by treatment group. Any scheduled pre-baseline data will also be summarized by visit and treatment group.

Plots of the mean over time will be displayed for each of the spirometry parameters listed above and all spirometry parameters collected will be included within subject listings.

Baseline for spirometry will be defined as the 60-minute pre-dose values at Visit 4. On all other dosing days the values recorded at 60 minutes pre-dose will be summarized. In case of multiple measurements at 60 minutes pre-dose (unexpected), the average of these will be used for baseline and the best (maximum) of these values will be used at the post-baseline timepoints. On all non-dosing post-baseline days the best (maximum) of the 2 measurements performed will be summarized.

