3.2 Study Activities

One day prior to visits that include a spirometric and/or clinical chemistry assessments, the site will contact the subject to remind them of the following study rules:

- To withhold all asthma medications the day of the study visit, or for at least 6 hours prior to start of study assessments.
- To fast (except for water) and refrain from vigorous exercise for at least 9 hours before a visit that includes a clinical chemistry assessment.
- Refrain from ingestion of leafy vegetables such as lettuce, spinach, kale and beetroot for 9 hours before visits.

At the start of each study visit, prior to any study procedures being performed, site personnel must confirm the subject withheld all asthma medications, including short-acting and -long-acting bronchodilators, for at least 6 hours before coming into the site, by confirming the last time of dosing for all asthma medication. Subjects who inadvertently took asthma medication within 6 hours of the start of study procedures must have their clinic visit delayed to later in the 6 AM to 10 AM window or rescheduled within the specified visit window.

The preferred order of assessments at all visits will be ECGs, vital signs, blood draws, FeNO, and lastly spirometry as appropriate for the study visit. Blood draws should ideally be performed in the morning to minimise diurnal variation in the level of eosinophils.

For all study visits, all PK and PD assessments (with the exception of spirometry) will be conducted between 6 AM and 10 AM to minimize the impact of diurnal variations on biomarker assessments. The site should make every effort to assess subjects at approximately the same time of day throughout the study and to dose subjects during the morning hours.

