^m At Visit 5 (D2), Visit 6 (D4), Visit 16 (D86), Visit 17 (D88), Visit 18 (D92) and Visit 19 (D99) blood samples for haematology including eosinophils will only be collected for participants enrolled in Cohort 4.

ⁿ At Visit 5 (D2), Visit 6 (D4), Visit 16 (D86), Visit 17 (D88), Visit 18 (D92) and Visit 19 (D99) FeNO will be performed only for participants enrolled in Cohort 4.

^o For subjects enrolled in Cohort 4, Visit 15 (WK12) will be handled as a non-dosing visit. All Visit 15 (WK 12) assessments/activities will be performed as they would on a non-dosing visit. Activities directly related to dose administration and post-dose observation (admission, study drug administration, 4-hour observation, assessment of injection site reactions and discharge) will NOT be performed.

The timing of vital sign, ECG, and spirometric assessments on dosing days is presented in Table 9.

Table 9 Timed Assessments at Each Dosing Visit

Clinical Variable	Pre-dose		Post-dose			
	-60 minutes (±15 minutes)	-30 minutes (±15 minutes)	30 minutes (±15 minutes)	1 hour (±15 minutes)	2 hours (±30 minutes)	4 hours (±30 minutes)
Vital signs	X		X	X		X
Electrocardiogram	X				X	
Spirometry	X	X	X ^a			

^a Spirometry will be obtained 30 minutes after the last injection is administered and may also be conducted at subsequent dosing visits if paradoxical bronchospasm is suspected.

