6 STUDY EFFICACY ASSESSMENTS AND PROCEDURES

6.1 Pharmacodynamic Assessments

The assessments described in this section will be conducted to assess asthma-related PD biomarkers. Samples will be collected as indicated in Section 3.3; the actual date and time of each sample collection will be recorded in the eCRF. Blood sample collection, handling, and storage will be described in the specimen collection and processing instructions. Blood samples for biomarker analysis will be taken and frozen. The decision to assay the frozen samples will be based on results from earlier sample analyses.

On dosing days, all PD assessments must be completed prior to initiation of the study drug administration.

Numerous cytokines are involved in the pathogenesis of asthma and several additional biomarkers have been associated with asthma activity (Custovic, Siddiqui et al. 2022). Several approved or in development asthma medications target cytokines (Lambrecht, Hammad et al. 2019).

Plasma levels of IL-5, IL-13, IFN λ , IL-17A, eotaxin-3, IP-10 (C-X-C motif chemokine ligand 10), and TSLP will be measured using ultrasensitive assays. Tryptase, carboxypeptidase, and TARC will also be measured. CRP, and total IgE will be assayed by the central clinical laboratory.

Initially, select samples from those collected will be analysed and the resulting data assessed. Following this, should analysis of the remaining samples be deemed informative, they too will be analysed.

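### SAP 10.11.2 places FeNO under spirometry rules for baseline and visit value that do not fit how FeNO is measured

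*SAP*

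**What the plan says.** SAP 10.11.2 (Spirometry) opens by grouping FeNO with lung function: "FeNO and other spirometry parameters (FEV1, FEV1%, FVC and PEF) will be summarized by visit". The rules that follow make no exception for FeNO:

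- Baseline: "Baseline for spirometry will be defined as the 60-minute pre-dose values at Visit 4".
- Later dosing days: "On all other dosing days the values recorded at 60 minutes pre-dose will be summarized". Unexpected repeats at that time are averaged at baseline, but the maximum is taken after baseline.
- Other days: "On all non-dosing post-baseline days the best (maximum) of the 2 measurements performed will be summarized".

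The protocol keeps the two procedures apart. FeNO is described in 6.1.1 as a biomarker of airway inflammation and spirometry in 6.3. Section 2 lists FeNO with blood eosinophils and puts FEV1 under a separate item. Section 3.2 sets a sequence: "The preferred order of assessments at all visits will be ECGs, vital signs, blood draws, FeNO, and lastly spirometry". Section 3.3 says: "The timing of vital sign, ECG, and spirometric assessments on dosing days is presented in Table 9"; FeNO has no row in that table. For FeNO on dosing days, Section 6.1 requires only this: "On dosing days, all PD assessments must be completed prior to initiation of the study drug administration". The default in Protocol 9.4.1, which applies unless something else is specified, is that "baseline is defined as the last observed measurement, whether scheduled or unscheduled, prior to the first dose of study drug". SAP 10.11.1 gives biomarkers the same kind of baseline, but its list of biomarkers leaves FeNO out.

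**The concern.** A rule written for FEV1 has been applied, by its position in the text, to a measurement with a different schedule and the opposite direction of benefit. FeNO change and percentage change from baseline are planned tables for both the administrative interim and the final analysis (SAP 13.2). Both need a baseline that FeNO can have and a visit value that does not favour the less healthy reading. As the text stands, two programmers could derive different FeNO baselines and each could cite the SAP. If a site records repeat FeNO values, the stated rule keeps the higher one after baseline, which would make a fall in FeNO look smaller.

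**Working it through.** The plan gives no figure to reproduce here. The check sets the passages side by side, with one illustrative calculation.

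**1. Which baseline rule governs FeNO?** SAP 10.1.1 limits its general last-non-missing baseline to safety endpoints and refers efficacy endpoints to their own sections. FeNO is named in 10.11.2 and is absent from the list in 10.11.1, so the direct route leads to the 60-minute spirometry rule. Pointing the other way, the SAP's summary of protocol version 8.0 calls FeNO a biomarker, its table titles in 13.2 begin with the biomarker label (though the other spirometry tables carry the same label), and 10.11.1 gives all biomarkers the last non-missing result before first dose. The SAP supports both readings.

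**2. Can FeNO meet the 60-minute rule?** Protocol Table 9 assigns the readings 60 and 30 minutes before dosing to spirometry. FeNO is scheduled on Day 1 (Table 5) and must precede dosing, but it has no time slot relative to the dose. A pre-dose value is planned for every subject; a reading defined as the 60-minute one is not.

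**3. Is there a fallback?** FeNO is also measured at Visits 1 and 2 (Table 4). Under Protocol 9.4.1 or SAP 10.11.1, a missing Day 1 FeNO would be replaced by the Visit 2 value. Under SAP 10.11.2 it would not. With 6 active subjects per cohort, one lost baseline is 1/6 = 16.7% of that group.

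**4. Can FeNO meet the maximum-of-two rule?** Protocol 6.3 and the schedule footnote on spirometry specify two assessments 30 minutes apart for spirometry only. No number of FeNO readings is stated. In Cohort 4, FeNO is scheduled on D2, D4, D86, D88, D92 and D99, none of which has spirometry in Tables 5 and 8, so those days have no scheduled pair of any kind.

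**5. What does the rule do if repeats exist?** Protocol 6.1.1 uses FeNO as a marker of the degree of airway inflammation, so the maximum is the worse value. For two independent normal readings with mean m and within-session SD s:

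E[max] − m = s/√π = 0.564 s

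A single reading, or the mean of repeats, has expectation m. With either at baseline, the rule therefore shifts the mean change from baseline upward by 0.564 s. The values of s below are assumptions:

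| Assumed s (ppb) | Shift 0.564 s (ppb) | Simulated, 1,000,000 pairs |
|---|---|---|
| 1 | +0.56 | +0.565 |
| 2 | +1.13 | +1.131 |
| 4 | +2.26 | +2.257 |
| 6 | +3.39 | +3.387 |

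In the same simulation the mean of the two readings was within 0.003 ppb of the true value. With one reading per visit the maximum is that reading and the shift is 0.

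**The case against.** The strongest reply is that this is a matter of placement and a sensible programmer would get it right. The baseline sentence refers to spirometry, every subject has a planned pre-dose FeNO on Day 1, and the last-pre-dose rule is available in both documents. This largely stands. A reader might infer from SAP 10.11.2 that no subject has a FeNO baseline; the documents do not support that, because the biomarker labels and the other baseline rules compete with it. Ambiguous is the right description.

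A reader might also infer that FeNO is summarized by its maximum throughout, so that every FeNO reduction is understated. That is not supported either. The maximum covers non-dosing days and unexpected repeats after baseline, and has no effect unless more than one FeNO value is recorded, which no schedule calls for. Even with repeats, a shift common to all groups would leave the active-placebo difference unchanged if s is the same in each group, or the ratio unchanged if s is proportional to the mean. The planned change-from-baseline summaries within each group would still be shifted.

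Three smaller points also stand. Protocol 9.4.1 allows a different baseline to be specified and 9.4.9 leaves exploratory PD analyses to the SAP, so the departure is permitted; noting it in Section 11 is good record-keeping. Nothing suggests that Day 1 FeNO will often be missing, since subjects are housed at the site. And the table shells in SAP Section 14, not reproduced in the public document, may hold further detail.

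The reply does not remove the main problem: the text names FeNO, gives it rules, and those rules do not match its schedule or its direction.

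**Conclusion.** The point holds as a rule that does not fit its endpoint. FeNO's baseline is ambiguous between a 60-minute reading that no FeNO schedule defines and the last pre-dose value used elsewhere, and only the latter allows the Visit 2 fallback. The maximum-of-two rule presupposes pairs scheduled for spirometry alone and points the wrong way for FeNO. Its size is 0 with one reading per visit, and about 0.56 times the within-session SD upward with two. The second figure assumes independent, normally distributed duplicates and a baseline that is a single reading or a mean; neither the number of readings nor the SD is in the documents. FeNO is an exploratory endpoint and SAP 10.1.4 plans no formal statistical analysis, so no primary or safety conclusion is affected. The change is worth making before unblinding because FeNO is tabulated at both the interim and the final analysis.

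**What to change.** 1. Move FeNO from SAP 10.11.2 to 10.11.1 and add it to the biomarker list there, with baseline as the last non-missing FeNO before first dose, so that Visit 2 serves if the Day 1 value is missing.
2. State how many FeNO readings are taken per visit. Use the recorded value, or the mean of any repeats, by the same rule at baseline and at follow-up, including the Cohort 4 days without spirometry.
3. Restrict the 60-minute and maximum wording in 10.11.2 to FEV1, FEV1%, FVC and PEF, so that each listed lung-function parameter keeps a rule.
4. Record the change in SAP Section 11 and check that the table shells agree.

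The cost is a few sentences in the SAP, with no new data and no change to study conduct.
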